9.2.1. Analysis of Primary Endpoint

The proportion of subjects with parasitological response (PCR corrected) at Day 28 post first dose of study medication will be estimated for the primary endpoint using the MITT and PP subject populations. The proportion will be estimated from the Kaplan-Meier curve based on the time to the first occurrence of parasitological failure (PCR corrected). Use of the Kaplan-Meier curve/product limit estimator is recommended by WHO⁸ and has been used in analyzing primary efficacy endpoints in late stage antimalarial treatment clinical trials.⁹²⁻⁹⁴

A subject will be a parasitological responder if she has a zero parasite count on the Day 7 visit without subsequent recrudescence (PCR corrected) through the day of consideration, otherwise she is a parasitological failure. In addition, subjects who withdraw from the study treatment during the first three days due to development of malaria symptoms and are administered antimalarial standard of care treatment for malaria in pregnancy, will be considered parasitological failures. The time (number of days) to the first occurrence of parasitological failure will be the analysis variable. The time in days is defined as [date of the parasitological failure event – date of the first dose of study medication + 1].

Subjects who do not experience the defined event (parasitological failure) will be censored as follows:

- Subjects who withdraw from the study early due to any reason will be censored on the day of the last available blood smear measurement;
- Subjects who continue on in the study but have all remaining blood smears missing from a given point in time onward will be censored on the day of the last available smear;
- Subjects completing the Day 42 visit post first dose of study medication will be censored on the day of the last available blood smear measurement;
- Subjects receiving any concomitant antimalarial for reinfection (PCR corrected) or in the absence of parasitemia will be censored at the visit date if the antimalarial is given after collection of the blood smear on that day. Otherwise the subject will be censored on the day of the last available previous blood smear measurement;
- Subjects who are lost to follow-up without any follow-up blood smears will have a censored duration of 1 day.

The proportion of subjects with parasitological response (PCR corrected) at Day 28 (primary) will be estimated from the Kaplan-Meier curve and its standard error estimated by the Greenwood formula. If less than 100%, a two-sided 95% confidence interval for the estimated proportion of subjects with parasitological response will be computed.

Additional sensitivity analyses will also be performed using the MITT and PP subject populations. The sensitivity analyses will consider premature discontinuation due to any reason as parasitological failure, if not already a parasitological failure due to a defined event. The same statistical methods will again be used to estimate the proportion of subjects with parasitological response (PCR corrected) at Day 28.

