5.3.3. Administration

Study medication will be administered as open label treatment under supervision. Study medication will be dispensed by the investigator or the fieldworker (Section 5.3.2). AZCQ should not be administered on an empty stomach. Each dose should be administered with a glass of water. First and third doses will be administered under supervision by investigator during ANC visits. The second dose will be administered at home under the supervision of fieldworker(s).

Any dose that is vomited within 30 minutes of administration will be repeated. If vomiting re-occurs after re-dosing on Day 0, Day 1 and Day 2, the subject will not receive further study treatments and will be provided standard treatment for malaria in pregnancy. The standard ANC care including IPTp will be given to the subject per local ANC guideline. If this happens during the home visit on Day 1, subject will be asked to return to the study physician within next 24 hours and will receive standard treatment for malaria in pregnancy. The subject will be followed through Day 42 and for pregnancy outcomes after delivery or termination of pregnancy for EIU safety assessments.

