6.1.3. Days 2 Visit (at ANC clinic/center)

- Assess adverse events;
- Concomitant treatment history;
- Oral temperature;
- If a subject presents with symptoms of malaria (fever $>37.5^{\circ}\text{C}$, oral), no further AZCQ dose would be given. The subject would be immediately referred to the investigator for parasite counts and appropriate treatment for malaria in pregnancy as per national/ local guidelines;
- Administer treatment: third dose of AZCQ;
- Two blood samples (one for AZ and one for CQ and desethyl-CQ analyses) from the subjects who consented for PK analysis at each of the following timepoints: predose, 2 hours (as close to 2 hours as possible) and 8 hours (window: 4 to 12 hours). The exact date and time of blood sample collection will be recorded.

6.1.4. Follow-up Visits on Days 7, 14, 21, 28, 35, 42 at ANC clinic/center)

- Assess adverse events;
- Concomitant treatment history;
- Limited physical examination (only on Days 42);
- Oral temperature;
- Hemoglobin (with HemoCueTM) (only on Day 42);
- Thick and thin peripheral blood smears for parasite identification and counts (2 smears at each visit);
- If a subject presents with symptoms of malaria (fever $>37.5^{\circ}\text{C}$, oral), and has parasitemia (microscopy), she will receive standard antimalarial treatment according to the local treatment guidelines for malaria in pregnancy;
- A dried blood blot will be collected at each visit for potential molecular testings;

- Two blood samples (one for AZ and one for CQ and desethyl-CQ analyses) on Days 7 and 14 (a random time point) from the subjects who consented for PK analysis. The exact date and time of blood sample collection will be recorded;
- One blood sample (for CQ and desethyl-CQ analyses only) on Days 21 and 28 (a random time point) from subjects who consented for PK analysis. The exact date and time of blood sample collection will be recorded.

6.1.5. Unscheduled Visits through Day 42

Any subject who develops signs and symptoms of malaria (fever ($>37.5^{\circ}\text{C}$, oral) and new signs and symptoms of malaria including malaise, headache or abdominal pain at any time other than the scheduled visits through Day 42, will be required to report to the investigator/study staff immediately for further evaluation. Blood smears and blood blots will be collected. The subject will be treated with the current standard of care for malaria in pregnancy.

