6.2. Subject Withdrawal

Subjects may withdraw from the study at any time at their own request, or they may be withdrawn at any time at the discretion of the investigator or sponsor for safety, behavioral, or administrative reasons. If a subject does not return for a scheduled visit, every effort should be made to contact the subject. In any circumstance, every effort should be made to document subject outcome and pregnancy outcome, if possible. The investigator should inquire about the reason for withdrawal, request the subject to return all unused investigational product(s), request the subject to return for a final visit, if applicable, and follow-up with the subject regarding any unresolved adverse events.

If the subject withdraws from the study and also withdraws consent for disclosure of future information, no further evaluations should be performed and no additional data should be collected. The sponsor may retain and continue to use any data collected before such withdrawal of consent.

Unless a subject withdraws the consent or leaves the town/village, she should continue in the study for follow up visits through Day 42, and following delivery or termination of pregnancy for EIU safety assessment. Subject may be withdrawn from the study treatment (during the first three days) due to safety concerns (eg, adverse events, significant laboratory abnormalities, and contraindications of concomitant medications), but not from the clinical study per se unless the subject withdraws consent. The standard antenatal care including IPTp will be given to the subject per local ANC guideline. The circumstances and data surrounding these events should be clearly documented in the case report form. The

investigator must determine the primary reason for discontinuation. A discontinuation must be reported immediately to the Pfizer medical monitor or his/her designated representative if it is due to a serious adverse event (SAE).

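### Section 9.2.1 gives no outcome to a woman who receives another antimalarial before the Day 7 smear with parasitaemia not shown to be cleared, so clearance by that drug can count as an AZCQ response

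*Protocol*

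**What the plan says.** **Response (Section 9.2.1).** "A subject will be a parasitological responder if she has a zero parasite count on the Day 7 visit without subsequent recrudescence", up to the day being assessed; otherwise she is a failure. Nothing in this definition depends on what else she took before Day 7.

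**Early failure (Section 9.2.1).** One further group fails: "subjects who withdraw from the study treatment during the first three days due to development of malaria symptoms" who are then given standard malaria treatment.

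**Censoring for antimalarial use (Section 9.2.1).** "Subjects receiving any concomitant antimalarial for reinfection (PCR corrected) or in the absence of parasitemia will be censored at the visit date", or at the previous smear if the drug came before that day's smear. Section 9.2.2 keeps only the absence-of-parasitaemia part for PCR-uncorrected results.

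**Ways to receive another antimalarial before Day 7.**
- Vomiting again after re-dosing (Section 5.3.3): "the subject will not receive further study treatments and will be provided standard treatment for malaria in pregnancy". Follow-up continues: "The subject will be followed through Day 42 and for pregnancy outcomes after delivery".
- Unscheduled illness through Day 42 (Section 6.1.5): smears and blots are taken, and "The subject will be treated with the current standard of care for malaria in pregnancy".
- Safety (Section 6.2): "Subject may be withdrawn from the study treatment (during the first three days) due to safety concerns", while she stays in the study. The care named is: "The standard antenatal care including IPTp will be given to the subject per local ANC guideline".

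**Other analyses.** The primary endpoint is estimated in MITT and PP. PP requires all three days of study medication (Section 9.2). The sensitivity analysis in Section 9.2.1 scores premature discontinuation as failure, without saying whether this means leaving treatment or leaving the study.

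**The concern.** The primary objective (Section 2.1) is the clearance rate of AZCQ. Section 9.2.1 already tries to keep other antimalarials out of that rate: it fails women treated for early symptoms and censors some other use. Section 5.3.3, however, creates a group that neither rule reaches. A woman who could not keep AZCQ down and was cleared by a different drug is scored as an AZCQ success. If no recrudescence follows, she remains one at Day 28 and at every secondary time point. The error runs in one direction only, in favour of the drug, in a primary population of a study meant to support regulatory submissions.

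**Working it through.** **Step 1. Apply the rules to repeat vomiting (Section 5.3.3).**
- Failure rule: not met. She stopped for vomiting, not malaria symptoms.
- Antimalarial censoring: not met. Her entry smear was positive (Section 4.1) and the Schedule of Activities has no smear between Day 0 and Day 7, so absence of parasitaemia has not been shown. Genotyping is done only on a positive smear after initial clearance (Section 7.1), so she cannot be classed as reinfected.
- Withdrawal and loss-to-follow-up censoring: not met. She is followed to Day 42.
- Result: with a zero Day 7 count and no later recrudescence she is a responder in MITT.

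**Step 2. Apply them to unscheduled illness (Section 6.1.5).**
- Study drug stopped for malaria symptoms in the first three days, then treated: already a failure.
- Smear-negative and treated: already censored.
- Smear-positive and treated after the last dose but before Day 7: neither rule applies. She has had three days of drug, so she is in PP as well.

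**Step 3. Apply them to safety withdrawal (Section 6.2).** No rescue course and no date are named. She is in the gap only if an antimalarial is in fact given before Day 7 with parasitaemia present or unknown.

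On every route, a woman still positive at Day 7 is a failure.

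**Step 4. Size.** The protocol has no figure for rescue before Day 7, so there is none to reproduce. Inputs:
- N = 166 (Section 9.1).
- r = 95%, the response rate in the other women, taken from the Section 9.1 planning value.
- k = number of women in the gap (assumed), and f = k/N.
- All k are assumed smear-negative at Day 7 without later recrudescence. Other censoring is ignored.

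Formulas:
- As written: r(1 − f) + f
- Censored at the smear before the other drug: r
- Counted as failures: r(1 − f)
- Overstatement: f(1 − r) against censoring, f against failure

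| k | f = k/166 | As written | Censored | Failures | Excess over censoring | Excess over failure |
|---|---|---|---|---|---|---|
| 3 | 1.8% | 95.1% | 95.0% | 93.3% | 0.1 points | 1.8 points |
| 8 | 4.8% | 95.2% | 95.0% | 90.4% | 0.2 points | 4.8 points |
| 15 | 9.0% | 95.5% | 95.0% | 86.4% | 0.5 points | 9.0 points |

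Example, k = 8: f = 8/166 = 0.048. As written, 0.95 × 0.952 + 0.048 = 0.952. As failures, 0.95 × 0.952 = 0.904.

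**Step 5. How plausible is k?** Section 1.3.2.3 gives 2% vomiting after one 1,000 mg azithromycin dose. That is any vomiting; Section 5.3.3 needs vomiting within 30 minutes and again after re-dosing. Assume 2% at each of three doses and a repeat probability of 2% to 50%. The rate is then 3 × 0.02 × 0.02 = 0.12% to 3 × 0.02 × 0.50 = 3%, or about 0.2 to 5 of 166 women. This covers repeat vomiting only and leaves out chloroquine's contribution. At k = 5, f = 3.0%: the excess is 0.05 × 3.0 = 0.15 points over censoring and 3.0 points over failure.

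**The case against.** **Much early rescue is already handled.** This stands. A reader might infer that every woman given another antimalarial before Day 7 escapes both rules. The text does not support that. Symptom-driven stops in the first three days fail, smear-negative unscheduled cases are censored, and Section 6.2 names only antenatal care including IPTp, while Sections 3 and 4.4 place IPTp with SP after Day 42.

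**PP and the sensitivity analysis protect the result.** This stands in part. PP drops women who miss a dose. It does not say whether a vomited dose counts as received, so repeat vomiting on Day 2 may stay in, and smear-positive women rescued after three doses do stay in. The sensitivity analysis helps if premature discontinuation covers stopping treatment. That is a natural reading but is not stated, and Section 6.2 separates the two. Either way it leaves the MITT primary estimate unchanged and misses women rescued after completing dosing.

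**Vomiting is intolerance, not parasitological failure.** This stands. A reader might infer that these women must be failures, by the logic of the symptom rule. That rule reflects illness on treatment, and scoring intolerance as failure could bias a clearance rate downward. Failure or censoring is the sponsor's choice of estimand.

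**The SAP may settle it.** The responder rule as stated gives a wrong result, so this is more than missing detail. Section 9 also requires major changes to the primary endpoint definition or its analysis to appear in a protocol amendment.

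**Conclusion.** The concern holds in a limited form. Section 9.2.1 lacks an outcome rule for a non-study antimalarial given before the Day 7 smear while parasitaemia is present or not shown to be cleared, unless study drug was stopped for malaria symptoms in the first three days. Repeat vomiting is the certain case, because the protocol itself prescribes it. Smear-positive treatment after the last dose and before Day 7 is the second. Safety withdrawal is conditional.

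The size depends on an unstated rescue rate. Over an assumed 3 to 15 women of 166 and r = 95%, the excess is 0.1 to 0.5 points against censoring and 1.8 to 9.0 points against failure. A reader might take the second range as the bias. It is that only if AZCQ would have failed in every one of these women, which the protocol gives no reason to assume. Against censoring, the excess is small beside the planned 5-point half width.

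This should be fixed before data are seen. It does not undermine the design: the study is single-arm estimation without a hypothesis test, and PP is reported alongside. Either explicit rule is better than counting these women as AZCQ responders.

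**What to change.** 1. In Sections 9.2.1 and 9.2.2, state that a woman given any non-study antimalarial before her first negative post-dose smear cannot count as a responder on later smears.
2. Give her one pre-specified outcome in the primary analysis: failure on the date of that antimalarial, or censoring at the last smear before it. Use the other as a sensitivity analysis.
3. State that premature discontinuation in the existing sensitivity analysis includes stopping study treatment.

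The cost is a few sentences in the statistical sections. The reported rate may be slightly lower, or rest on slightly fewer women. How the women are treated and followed does not change.

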9.2.2. Analysis of Secondary Endpoints

The secondary parasitological response endpoints will be analyzed in the same manner as the primary endpoint, and will use the ITT, MITT, and PP subject populations. These analyses will be done using both PCR corrected and uncorrected results, and will also include the sensitivity analyses.

For PCR corrected, censoring will be done in the same manner as for the primary endpoint. For PCR uncorrected, censoring will be as follows for subjects who do not experience parasitological failure:

- Subjects who withdraw from the study early due to any reason will be censored on the day of the last available blood smear measurement;
- Subjects who continue on in the study but have all remaining blood smears missing from a given point in time onward will be censored on the day of the last available smear;
- Subjects completing the Day 42 visit post first dose of study medication will be censored on the day of the last available blood smear measurement;
- Subjects receiving any concomitant antimalarial in the absence of parasitemia will be censored at the visit date if the antimalarial is given after collection of the blood smear on that day. Otherwise the subject will be censored on the day of the last available previous blood smear measurement;
- Subjects who are lost to follow-up without any follow-up blood smears will have a censored duration of 1 day.

For parasite counts, descriptive statistics (N, mean, SD, standard error, median, minimum and maximum) will be provided at each time point on actual counts.

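### Sections 9.2.1 and 9.2.2 censor at a non-study antimalarial only women who never fail later, so censoring depends on the future outcome; the expected bias is downward and small

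*Protocol*

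**What the plan says.** The primary estimate in Protocol section 9.2.1 is a Kaplan-Meier one: "The proportion will be estimated from the Kaplan-Meier curve based on the time to the first occurrence of parasitological failure (PCR corrected". A responder must be smear-negative on Day 7 and remain "without subsequent recrudescence (PCR corrected) through the day of consideration, otherwise she is a parasitological failure". That definition makes no exception for a recrudescence that follows a non-study antimalarial.

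The censoring list is introduced by "Subjects who do not experience the defined event (parasitological failure) will be censored as follows". One of its bullets reads "Subjects receiving any concomitant antimalarial for reinfection (PCR corrected) or in the absence of parasitemia will be censored at the visit date", with the last previous smear used instead if the drug was given before that day's smear. Section 9.2.2 uses the same kind of lead-in: "For PCR uncorrected, censoring will be as follows for subjects who do not experience parasitological failure". Its antimalarial bullet covers only drugs given without parasitemia.

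Non-study antimalarials are foreseen before Day 42. Under section 6.1.4 a symptomatic woman with parasites on microscopy is treated: "she will receive standard antimalarial treatment according to the local treatment guidelines for malaria in pregnancy". Section 6.1.5, on unscheduled visits for malaria symptoms, says "The subject will be treated with the current standard of care for malaria in pregnancy". Under section 6.2, unless she withdraws consent or moves away, "she should continue in the study for follow up visits through Day 42", so smears and genotyping after the antimalarial will exist.

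The sensitivity analysis at the end of section 9.2.1 recodes premature discontinuation as failure. It does not touch women who took an antimalarial and stayed in the study.

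**The concern.** Take two women who are clear of the original parasite and receive the same non-study antimalarial on Day 14. One recrudesces on Day 28. She has experienced the event, so no censoring bullet applies to her; she stays in the risk set and counts as a failure on Day 28. The other stays clear. She is censored at Day 14 and is missing from the Day 28 denominator. On Day 14 nothing distinguished them.

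Kaplan-Meier needs the women still at risk at each visit to represent those censored before it. Here a treated woman stays at risk only if she is going to fail. Later failures remain in the numerator while the matching successes leave the denominator.

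Two coherent rules exist: censor every woman at the antimalarial, or keep every woman at risk. The written text applies one to the women who stay clear and the other to those who fail. Estimation is this study's only aim, and two programmers reading the text differently could report different primary estimates from the same data.

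**Working it through.** **Inputs from the protocol.** About 166 women, about 10% dropout and a true response of at least 95% (section 9.1): 166 × 0.9 ≈ 149 evaluable. Smears weekly from Day 7 to Day 42. The protocol gives no figure for antimalarial use, so there is no figure of its own to reproduce on this point. For scale, the Wald half width is 1.96 × √(0.95 × 0.05 / 149) = 3.5 points, against a target of 5.

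**Assumed, not in the protocol.** Uptake of a qualifying antimalarial of 5-20%, unrelated to prognosis; failure risk after it either unchanged or halved; a true Day 42 response of 93%.

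**Worked case.** 149 women; 5 failures among untreated women; 10 women treated on Day 14, of whom 2 recrudesce on Day 28 (7 failures in all). The results depend slightly on when the other 5 fail, so both extremes are shown.

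| Rule | Other 5 fail on Day 28 | Other 5 fail on Day 7 | About |
|---|---|---|---|
| As written (8 censored on Day 14) | 134/141 = 95.0% | 144/149 × 134/136 = 95.2% | 95.1% |
| Keep all at risk | 142/149 = 95.3% | 142/149 = 95.3% | 95.3% |
| Censor all 10 on Day 14 | 134/139 = 96.4% | 144/149 = 96.6% | 96.5% |

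The written rule is below both. Its shortfall from keep-all is about 0.2 points. The remaining 96.5 − 95.3 = 1.2 points separates two coherent rules and reflects whether a recrudescence after another drug should count. That is an estimand choice, not an error. The case is also deliberately unfavourable: 2/10 treated women fail against 5/139 = 3.6% of the others.

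**A second case.** 149 women, 7 other failures by Day 28, 15 women treated on Day 14. If 1, 2 or 3 of the 15 fail on Day 28, the written rule gives 94.3%, 93.6% or 92.9%; keep-all gives 94.6%, 94.0% or 93.3%; censor-all stays at 95.1%. If none fails, the written rule and censor-all agree at 95.1%.

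**Expected size at Day 28, true 95%.** With post-antimalarial risk unchanged, both coherent rules target 95.0%, so the whole gap is the error. Simulated uptake of 5%, 10% and 20% by Day 21 gives 94.9%, 94.8% and 94.4% under the written rule, a shift of 0.1 to 0.6 points. With uptake by Day 28 instead, the figures are 94.9%, 94.8% and 94.5%. If the other drug halves later failures, the gap to censor-all at 10% and 20% uptake (by Day 28) is 0.1 (94.9 against 95.0) and 0.2 (94.8 against 95.0).

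**Day 42, true 93%.** At 20% uptake by Day 28 the written rule gives 92.0% with risk unchanged and 92.5% with risk halved.

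**Single trials of 149.** With 20% uptake and halved risk, the written Day 28 estimate differs from censor-all by −0.20 points on average: 60% of trials unchanged, 25% lower (at most 2.5 points) and 15% higher (at most 0.1 point). It can be higher because a treated woman who fails only on Day 35 or 42 stays in the Day 28 risk set as a success.

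**The case against.** The lead-in is ordinary protocol wording and may have been meant as has not failed by then. Section 9 leaves detailed methods to an Analysis Plan that is not at hand and may settle precedence between events and censoring. This is fair as to intent. But section 9.2.1 states a rule rather than leaving one open, and its failure definition, which has no exception after an antimalarial, supports the literal reading. If the milder meaning was intended, the fix merely records it.

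The uptake figures are assumptions. Standard IPTp with SP is deferred until after Day 42 (sections 3 and 4.4), and at scheduled visits treatment needs both symptoms and parasitemia. For the PCR-uncorrected endpoints such a woman has already failed, so only antimalarials given without parasitemia matter there. This stands. It limits the size, not the mechanism: treatment of reinfections, unscheduled visits and routine antenatal care after withdrawal from study treatment (section 6.2) remain as possible routes, with unknown frequency.

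A reader might infer that the response rates will certainly or materially be too low, or that the 1.4 points between 95.1% and 96.5% measure the error. Neither is supported. The direction holds in expectation only, and most of that gap is an estimand choice. A reader might also infer that recrudescence after another drug is wrongly charged to AZCQ. Section 7.1 treats recurrence of the original parasite as treatment failure, so counting it is defensible, provided the women who stayed clear after the same exposure are kept at risk too.

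**Conclusion.** The point holds as a flaw in a stated rule. As written, censoring at a non-study antimalarial is conditional on never failing later, in both 9.2.1 and 9.2.2, and the planned sensitivity analysis does not correct it. The expected bias is downward if antimalarial use is unrelated to prognosis and some women fail after it.

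The size is modest: about 0.1 to 0.6 points at Day 28 for 5-20% uptake, well inside the 3.5-point half width, and larger at Day 42 (about 1 point at 20% uptake with risk unchanged). All of this rests on an uptake that the protocol does not give. No hypothesis is tested, so no decision threshold is at risk. It should be corrected because the fault lies in the primary estimator, few events are expected, and the repair costs almost nothing.

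**What to change.** In 9.2.1 and 9.2.2, take the antimalarial bullet out from under the conditional lead-in and apply one rule to every woman. In line with the plan's evident intent to censor, state that:

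- for every woman who has not failed by then, follow-up for the endpoint ends at her first non-study antimalarial given for reinfection (PCR-corrected endpoints only) or without parasitemia, whatever later smears show;
- the existing choice between that visit's smear and the previous one still sets the censoring date;
- only failures on or before that date count as events.

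Add a sensitivity analysis that ignores these antimalarials and keeps all women at risk to their failure or last smear. Reporting both shows the estimand choice openly.

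The cost is a few sentences, with no new data and no change to any clinical rule. Section 9 asks for a protocol amendment if the change is judged a major modification of the primary analysis. The downside is that a few recrudescences after another antimalarial leave the main estimate; the sensitivity analysis shows them.
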